## Study Application (Version 1.12)

### 1.0 General Information

**\*Please enter the full title of your study::**

Effect of antibiotics on submucosal enteric neurons and glia in the lower gastrointestinal tract.

**\*Please enter the study short title:**

Antibiotics effects on enteric neurons and glia.

\* This field allows you to enter an abbreviated version of the Study Title to quickly identify this study.

**Is this Study using Subject Management?**

☒ Yes ☐ No

### 2.0 Add departments

**2.1 List departments associated with this study:**

- Please choose at least two labs/departments. Your main lab/dept. should be the primary lab listed, e.g. your HOL's lab.
- All protocols must also list "Rockefeller University Hospital (RUH)" as a secondary lab/dept.
- You may also list additional, lab/dept(s) if appropriate to include RU collaborators.
- If your lab/department is not listed in the 'Add Department' dropdown menu, please contact RUH IT at [hospital\\[contact]](mailto:[contact]) to arrange for the new lab to be added to the listing.

Is Primary?	Department Name
	RUH - Laboratory of Mucosal Immunology ([name])
	RUH - Research Facilitation Office (Facilitation)

**3.2 If applicable, please select the Research Staff personnel:**

A) Additional Investigators

Name	Role	Training Record
------	------	-----------------

### 3.0 Assign key study personnel(KSP) access to the study

No Additional Investigators have been added

### 4.0 Rockefeller University Conflict of Interest

**4.1 Investigator Financial Conflict of Interest** All KSP must complete an annual certification of their Significant Financial Interest ("SFI") disclosures in the University's online Research Administration System at <https://RAS.rockefeller.edu>. Disclosures also must be updated in connection with new human subjects research protocols ("Research Certification"), and within 30 days of discovering or acquiring a new SFI. To avoid delays in the IRB review process, when prompted by an email from [[contact]](mailto:[contact]) requesting an updated Research Certification, KSP should click on the Research Certification link contained in that email notification, or go to <https://RAS.rockefeller.edu>, to (a) review and update his or her SFI disclosures or certify that he/she has no updates, as appropriate, and (b) indicate whether any of his/her SFI disclosures are reasonably related to the design, conduct, or reporting of the research protocol. If a KSP discloses a SFI that might constitute a conflict of interest with respect to the proposed protocol, he or she must e-mail a copy of the Lay Summary of the draft protocol to [name], Esq. ([[contact]](mailto:[contact])). Doing so will facilitate addressing COI issues in step with the development of the study protocol. Non-compliance or tardiness in making or updating COI disclosures will result in a delay in IRB review. **Institutional Conflict of Interest:**

As early as possible the PI (or a designee) preparing a clinical research protocol must review a list of entities in which The Rockefeller University has an Institutional Financial Interest at <https://icoi.rockefeller.edu/account/login.php>. If the proposed study involves any entity on that list, the PI (or designee) must notify [name], staff to the FCOI Committee, by e-mail [[contact]](mailto:[contact]) and [name], Chair of the IRB, by email: [[contact]](mailto:[contact]), provide the name(s) of the entities and a copy of the Lay Summary. Doing so will facilitate addressing institutional COI issues in step with the development of the study protocol. Failure to take steps to review and address potential institutional conflicts of interest will delay the IRB review process.

## 6.0 Delegation of Authority

### 6.1 Enter authorized activities for all **Rockefeller University personnel** named on the study.

#### Activity Codes:

- |                                       |                                |   |
|---------------------------------------|--------------------------------|---|
| 1. Informed consent **                | 11. Participant recruitment    | 21. Skin biopsy *                         |
| 2. Inclusion / exclusion criteria     | 12. Perform assays             | 22. Conduct sleep study                   |
| 3. Medical/medication history *       | 13. Specimen / sample analysis | 23. Diet design and preparation           |
| 4. Perform Physical Exam *            | 14. Lumbar puncture *          | 24. Nutritional assessment and counseling |
| 4a. Write / Sign LIP orders *         | 15. Femoral line placement *   | 25. Addition of PABA to food              |
| 5. Skin assessments and photos        | 16. Central line placement *   | 26. Data analysis                         |
| 6. Study drug dispensing *            | 17. Insulin clamp procedure *  | 27. Data review                           |
| 7. Study drug administration *        | 18. Leukapheresis *            | 28. Data management                       |
| 8. Study drug reconciliation          | 19. Sigmoidoscopy *            | 29. Maintain regulatory documents / files |
| 9. Study drug compliance              | 20. Fat biopsy *               | 30. Complete CRF's                        |
| 10. Administer study questionnaire(s) |                                |   |

**Add up to three additional authorized activities specific to this study (do NOT add activities that have previously designated codes):**

31:	Facilitator
32:	
33:	

#### Activity Codes Continued:

- 34. Behavioral Testing
- 35. Bod Pod
- 36. Bone Marrow Aspiration \*
- 37. Neuropsychological Testing \*
- 38. Conduct Focus Group
- 39. Conduct Smell Study
- 40. Genetic Counseling \*
- 41. Apply EEG Electrodes \*\*
- 42. Olfactometer Test
- 43. Study Participant Teaching
- 44. Resting Energy Expenditure
- 45. Source Document Review & Correction
- 46. Medical Photography
- 47. See 4a
- 48. Adverse Event Assessment
- 49. Clinical Trial Registration
- 50. Study Support Drug Dispensary
- 51. Internal Monitoring
- 52. Randomization

**Enter delegation of authority for additional Rockefeller University Key Study Personnel:**

Name	Title	Authorized Activities	Start Date	End Date
No results found				

**Enter the authorized activities for External Personnel:**

Name	Title	Authorized Activities	Start Date	End Date
No results found				

## 7.0 Study Description

### 7.1

## Study Classification

Full Review

### 7.2

## \* Submission Request Category

**Note:** For each submission, please designate the level of review, or "Submission Request Category" you are requesting. When completing this field, please indicate the level of review you are requesting for the specific submission you are working on.

For example, if you are submitting an Expedited Amendment request to change the Key Study Personnel on your existing Full Board study, you should select "Expedited Review" in both the Amendment Submission Form and Study Application. The IRB will confirm an Expedited review of the Amendment submission is appropriate, and the overall study will remain classified as a full Board review. Please see the help bubble for guidance.

*To submit a request for a Not Human Subjects research determination, please exit this form and select the "Not Human Subjects Research Determination" form under Create a New Study.*

- ☐ Exempt from Review
- ☐ Exempt with Limited Review
- ☐ Expedited Review
- ☒ Full Review

### 7.3 \* Lay Summary

Please provide a summary of your study in lay language that is easily understood by a non-scientist. The summary should be no more than half a page (500 words or less) and should contain a clear statement of the rationale for the study.

Please click on the help bubble to get the information on " How to use iRIS text editor."

Please provide a summary of your study in lay language. The summary should be no more than a half page (500 words or less) and should contain a clear statement of the rationale for the study.

The interactions between bacteria and their products with the intestinal tissue are important for maintaining a healthy and balanced system. Alterations in gut bacteria communities have been associated with various human pathologies. Our lab and others have found that mice treated with short and long-term antibiotics exhibit a transient yet profound loss of neurons in the more superficial submucosal and deeper muscularis plexi in the intestine accompanied by slow motility. Glia cells also depend on microbiota for their maintenance. In humans, antibiotic use has been associated with disorders of gut-brain interactions (DGBI) such as irritable bowel syndrome however whether there are changes in the enteric neurons and glia cells remain unknown. Therefore, we propose to further characterize the neurons and glia populations in the human distal colon after a single antibiotic course. We expect that our study will reveal glia and neuronal subtypes that are susceptible to changes in the bacteria populations and depend on microbial products for their maintenance. Our findings will guide future DGBI studies to ascertain the physiological effects that such loss has on intestinal healthy balance.

#### 7.4

##### \* Public Health Impact Statement

Provide a brief plain language statement (100 words or less) of the value of the research proposed and its potential impact on population health. Additional instructions located in Help.

Anti-microbials have been associated with Disorders of Gut Brain Interactions (DGBIs). We propose to study the effects that antibiotic use has on the number and type of neuron and glia cells in the gut. A better understanding of these effects will lead to the development of new therapeutic interventions and prevention strategies.

#### 8.0

##### Clinical Trial Registration

#### 8.1

##### Clinical Trial Registration

The types of studies listed below must be registered at **Clinical Trials website** before enrolling the first participant in order to be in compliance with federal regulations and preserve the opportunity to publish the study in journals that adhere to the **ICMJE guidelines**. Please check the answer that best applies.

- ☐ Study involves testing of FDA regulated drugs or biologics (See HELP)
- ☒ Study is funded by the NIH, and meets the definition of a "clinical trial" (see HELP)
- ☐ Study meets the ICMJE definition of a "clinical trial" (See HELP)
- ☐ Additional funding agency or journal requires clinical trial registration
- ☐ None of the above

If you selected 1, 2, 3, or 4 you must register your trial with ClinicalTrials.gov through the Rockefeller University institutional account. Please contact the Clinical Research Support Office [name] for assistance.

## 9.0

### Study Overview/Summary

#### 9.1 \* Who initiated this study?

Please specify one:

- ☒ Principal Investigator Initiated  
☐ Industry Initiated  
☐ Other

#### 9.2 \* Are other institutions involved in the study?

- ☒ No  
☐ Yes

#### 9.3 \* Is this a multi-site trial using a single IRB (sIRB) review arrangement? Please see help bubble for definition.

- ☐ Yes ☒ No

#### 9.4 \* Who (What) is to be studied?

- ☒ Human Subjects - including coded samples and/or data with links to Identifiers  
☐ Deidentified Samples - unable to be linked to identifiers by receiver  
☐ Data Only - unable to be linked to identifiers  
☐ Identifiable samples or data for exemptions (per 104 (s)(4))

#### 9.5 \* Study Type:

- ☒ Interventional  
☐ Observational

#### 9.6 The initial date of IRB approval/determination was:

12/01/2022

#### 9.7 \* What is the expected duration of the study?

7 years

#### 9.8 \* Are any of the following agents to be used in the study?

Check all that apply:

- ☐ FDA Approved Drug
- ☒ FDA Approved Drug for Off-Label Purpose (This might require an IND)
- ☐ Investigational New Drug
- ☐ Biologic Agents
- ☐ Nutritional Supplements
- ☐ Placebo
- ☐ Vaccines
- ☐ No Agents
- ☐ FDA Exemption to use Study Drug

Please indicate whether your application to the FDA for use of the investigational drug is planned or has been submitted by checking the box below.  
Include a description of the status of the FDA submission in the text box.

- ☐ Planned
- ☐ Submitted

#### 9.9 \* Are investigational devices to be used in the study?

☐ Yes ☒ No

#### 9.15 Special Research Procedures

Does the study propose to directly involve participants in the following special research procedures?

- ☐ Recombinant DNA
- ☐ Gene Therapy
- ☐ Fetal Tissue
- ☐ Embryonic Stem Cells
- ☐ Induced Pluripotent Stem Cells
- ☐ CRISPR-Cas9

If any item is checked, please see Help for details.

#### 9.16 \* Radioactive Isotopes Involved

Will participants be exposed to any radiation other than routine x-rays solely for clinical care purposes?

☐ Yes ☒ No

### 10.0 Interventional

#### 10.1 \*Interventional, please specify:

- ☒ Open Label
- ☐ Single Blind
- ☐ Double Blind
- ☐ Other

## 11.0 Study Phase:

### 11.1 Study Phase:

Select where applicable

- ☐ Phase 0
- ☐ Phase I
- ☐ Phase I/II
- ☐ Phase II
- ☐ Phase III
- ☐ Phase IA
- ☐ Phase IB
- ☐ Phase IIA
- ☐ Phase IIB
- ☐ Phase IB/IIA
- ☐ Phase IIB/IIIA
- ☐ Phase IIIA
- ☐ Phase IIIB
- ☒ N/A

## 12.0 Objectives and Rationale

### 12.1 \* Overview

Briefly state the ***purpose of this study***. Give enough background and rationale to provide both scientists and lay members of the IRB and ACCTS with the basis for exposing human participants to the risks involved.

The enteric nervous system (ENS) has been recognized as the “second brain” as it can regulate enteric physiology without central nervous system input. Similar to the central nervous system, it is composed of multiple neuron populations whose main functions are gut motility, secretion, and absorption [3, 10]. In addition to the neurons, the ENS contains glia cells whose main role is neuroprotection but also contribute to normal gut motility [11]. Several studies have demonstrated that the microbiota and the ENS have an intimate relationship that begins *in utero*, and it is critical for its normal development [3]. Neurons can recognize bacteria and their products [12, 13]. Our lab and others have shown neuronal loss after enteric infections and antibiotic (Ampicillin) treatment in the muscularis layer, that results in delayed transit time in animal models [5, 7]. Hence, communication between the microbiota and the ENS is important to maintain normal gut motility. Disorders of Gut-Brain Interactions (DGBIs) are quite common, among these are Irritable Bowel Syndrome (IBS defined by Rome IV criteria as abdominal pain associated with a change in consistency and frequency of bowel movements) and the constipation predominant subtype (less than 3 bowel movements per week) is the most prevalent, which is also the most common motility disorder that our mouse models of infection and antibiotics treatment exhibit [14]. IBS has been associated with dysbiosis and a recent study demonstrated that antibiotic use immediately before or after screening colonoscopy increased the risk of developing IBS [9, 15]. In addition, dysfunction of submucosal neurons in IBS has been previously reported but whether there are changes in neuron numbers or neuron characteristics has not been

explored [16]. While there have been prospective studies that have explored the effects of antibiotics in patients treated for *Helicobacter Pylori*, there have been other investigators who have focused on the long term effects of antibiotics in healthy volunteers [17,18]. Therefore, similar to our animal models, we propose that humans experience a profound and transient loss/alteration of neurons in the setting of antimicrobial use associated dysbiosis that manifest as DGBIs, most notably the constipation subtypes. This proposal will address **whether antimicrobial use leads to quantitative and qualitative changes in the populations of submucosal neurons and glia cells in human subjects**.

We will test this hypothesis in a prospective study in which healthy participants will be asked to take the commonly used antibiotic amoxicillin twice a day for 7 days, and colon tissue biopsies will be obtained before and after treatment. We will then process and analyze the human tissue using techniques already established in the lab that will include confocal microscopy to visualize structural changes, single nuclei RNA sequencing, 16S ribosomal bacteria RNA sequencing and metabolomics analysis.

#### 12.4 \* Engaging Stakeholders: Describe any plans to engage other stakeholders (Scientists, practitioners, patients, advocacy groups, etc.) for hypothesis generation, or feasibility purposes.

Since this is a human subjects protocol we plan to engage the assistance of Rockefeller Hospital Research Support Office for protocol development, and recruitment of participants. We will need the assistance of a pharmacist to dispense the antibiotics. The hospital staff will assist with volunteers' visits and the endoscopic procedures. In the lab, one postdoc will assist with planning sequencing strategy. Staff from metabolomics, genomics and bioinformatics research support cores will also assist in this project.

Because we will only recruit healthy participants for this study, we will not engage any patients' groups.

#### 12.5 \* Hypothesis

Describe the **research hypothesis** in a single sentence.

Antimicrobial use leads to quantitative and qualitative changes in the populations of submucosal neurons and glia cells in human subjects.

#### 12.6 \* Aim(s)

Indicate how you will **address the hypothesis** (e.g., to compare groups, to estimate a parameter, to ascertain feasibility). Since the sample size determination is usually based on the primary aim only, the primary aim should be sufficient to justify the study.

Aim1: Characterize the changes of submucosal neurons and glia cells before and after course of antibiotics in humans.

#### 12.7 \* Primary Outcome(s)

Indicate which **variable(s)** will be assessed to judge the primary specific aim. Give measurement units, if applicable.

Total number of colonic submucosal neurons and glia cells in humans before and after course of antibiotics.

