**VISIT #2: Procedure Visit ( 2 to 21 days after screening visit) (approximately 2 hours; Day Patient Visit)**

- Stool sample will be collected and stored in the refrigerator.
- Vital signs pre- and post-procedure. Post-procedure, vital signs will be taken immediately after the procedure, then 30 minutes after the procedure, and 1hr after the procedure.
- POC Urine Pregnancy test for women of childbearing age.
- Stool consistency and frequency questionnaire will be given to the participant to complete.
- Oral diazepam 5 mg pre-procedure will be offered and administered based on the patient preference and PI evaluation. Oral diazepam takes 30 - 60 minutes to take effect.
- Tap water enema upon arrival followed by additional 1 or 2, 200ml tap water enemas if the participant still has solid debris after a bowel movement.
- Flexible Sigmoidoscopy Procedure
  - The sigmoidoscope is advanced to the beginning of the descending colon (about 24 cm) and up to 20 biopsies will be obtained with Boston Scientific Jumbo forceps (max diameter of 2.8mm), each biopsy will be 2-2.8 mm in size, one in each quadrant, spaced 2-3cm throughout the sigmoid colon.
  - Tissue specimens will be placed in sterile specimen cups containing normal saline.
- Observation for one-hour post-procedure (for signs of bleeding or distress) and evaluation by nursing and PI to determine when ready for discharge.
- Breakfast
- Post-procedure Instruction sheet given prior to departure.

In the event a mass, polyp, or ulceration is found, a copy of the images obtained during the sigmoidoscopy and a letter with the examination findings will be given to the participant and they will be instructed to follow-up with their Primary Healthcare Provider.

The participant will be asked to return in two weeks for Visit #3 and instructions on avoiding the addition of new probiotics, prebiotics or drastic dietary changes will be given. In addition, participants will be instructed to notify us if he/she starts any antimicrobial medication including antifungals, or developed any intestinal infection.

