#### Lab Procedures

Sample processing and analysis.

A total of 20 biopsies will be obtained per participant: 4 will be used for tissue immunostaining and remaining 16 will be used for single nuclei sequencing. Tissue obtained from each region will be separated: four biopsies will be pinned and fixed in 4% paraformaldehyde overnight, followed by washing, permeabilization, and staining of the tissue with the neuronal antibody ANNA-1 and anti-Sox10 which is a glia antibody. We will image the samples with a confocal microscope, and we will count the neurons and glia. Sixteen biopsies will be snap frozen in liquid nitrogen and stored in a -80C freezer. Once several samples have been collected, we will defrost them and further process them into single nuclei suspensions that will be utilized to generate sequencing libraries with the 10X Chromium platform. We will sequence the nuclear RNA to determine the expression of multiple genes in the human intestine. Of note, we do not know what the nuclei yield will be for the pooled 16 biopsies obtained per participant, our target nuclei count will be about 20,000 in total. We will enrich the desired populations by staining the nuclei with anti-NeuN and anti-Sox10 to sort the neurons and glia populations respectively. We do not know what will be the proportions of the different cell types for this particular protocol, however, based on other studies we expect small proportion of glia and neurons thus making it necessary to pool samples from several participants. We will not sequence the human DNA. We will isolate bacterial DNA from the stool and perform 16S ribosomal RNA sequencing for which we have an optimized protocol in our lab. Moreover, we will identify and measure stool metabolites via Liquid Chromatography- Mass Spectrometry at RU Proteomics Core.

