**12.10 \* Data Analysis**

Describe method(s) of data analysis.

In this pilot study, with 10 participants, we will assess the change in the outcomes between baseline and follow up using a paired sample t-test. While exploratory, we will be able to detect a 1.3 standard deviation change in outcomes pre versus post, with greater than 80% power, holding Type I Error to 5%.

**12.11 \* Explain the rationale for the choice of statistical measures and the number of participants proposed for the study, including the power calculations when applicable.**

Assuming we can enroll 10 patients, we will have over 80% power to detect a 1.3 standard deviation difference in continuous outcome measures and a 38% absolute difference in proportions (assume base rate of 50%). This pilot study will also provide observed effect size for use in the design of future analysis.

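### The primary outcome is a raw cell total with no unit or denominator, although the amount of tissue counted is not held constant

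*Combined protocol and SAP*

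**What the plan says.** The form's prompt for the primary outcome includes "Give measurement units, if applicable". The entry in Section 12.7 is "Total number of colonic submucosal neurons and glia cells in humans before and after course of antibiotics". No unit follows.

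Section 12.9 describes the sampling in the same terms at Visits 2, 4 and 5: "up to 20 biopsies will be obtained with Boston Scientific Jumbo forceps", and "each biopsy will be 2-2.8 mm in size, one in each quadrant, spaced 2-3cm throughout the sigmoid colon". Under Lab Procedures it continues: "A total of 20 biopsies will be obtained per participant: 4 will be used for tissue immunostaining". The counting step is one sentence: "We will image the samples with a confocal microscope, and we will count the neurons and glia".

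Section 12.10 gives the analysis: "we will assess the change in the outcomes between baseline and follow up using a paired sample t-test".

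The outcome, laboratory and analysis sections contain no area, volume, per-field or per-ganglion denominator. They set no minimum amount of submucosa for a usable biopsy and give no rule for a biopsy that contains none.

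**The concern.** The number of cells counted is cell density multiplied by the amount of submucosa examined. The hypothesis in Section 12.5 concerns the cell populations, so only the first factor is of interest. With a raw total, the second factor goes straight into the pre/post difference. Two biopsies with identical density, both within the permitted size range, can give quite different counts.

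Two consequences need to be kept apart. Random variation in tissue quantity widens the spread of the differences, which matters with 10 participants. A systematic difference in tissue quantity between visits would shift the mean difference itself, and a paired comparison of totals cannot separate that from a change in the tissue.

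**Working it through.** **The plan's own figure.** Section 12.10 claims more than 80% power for a 1.3 SD change with 10 participants. For a two-sided 5% paired t-test, taking 1.3 as a multiple of the SD of the differences, the noncentral t distribution gives 95.4%, so the stated bound is met. The figure is in SD units and the documents give no SD for a count or a density. It therefore neither depends on the unit of the outcome nor shows how much power tissue variation would cost.

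**Inputs from the documents.** Biopsy size 2 to 2.8 mm (Section 12.9, Visits 2, 4 and 5); four stained biopsies (Lab Procedures); 10 participants and a paired t-test (Section 12.10).

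**Assumptions not in the documents.** Count proportional to face area; diameter D uniform over 2 to 2.8 mm and independent between biopsies; full-face imaging.

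**Step 1, range of face area.** (2.8/2)² = 1.96.

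**Step 2, random size variation.**
- Mean of D²: (2.8³ − 2³)/(3 × 0.8) = 13.952/2.4 = 5.813.
- Mean of D⁴: (2.8⁵ − 2⁵)/(5 × 0.8) = 140.104/4 = 35.026.
- Variance of D²: 35.026 − 5.813² = 1.231, so the SD is 1.110.
- CV for one biopsy: 1.110/5.813 = 19.1%.
- CV for a total of four: 19.1%/√4 = 9.5%.
- One participant's difference between two visits: 9.5% × √2 = 13.5% of the mean total.
- Mean difference over 10 participants: 13.5%/√10 = 4.3%.

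A simulation under these assumptions gives the same CVs (0.191 for one biopsy, 0.095 for four). With no true change and no systematic size difference, the two-sided 5% paired t-test on totals rejected in 4 to 5% of simulated trials. Random size variation therefore adds noise and does not produce false findings.

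**Step 3, a systematic size difference, as a what-if.**
- Mean diameter falls from 2.4 to 2.2 mm between visits: 1 − (2.2/2.4)² = 16% apparent loss with density unchanged.
- Mean diameter rises from 2.4 to 2.6 mm: (2.6/2.4)² = 1.174. A true 15% loss of density would then give 0.85 × 1.174 = 1.00, that is, no visible change.
- With the 16% area shift, no true change, n = 10 and four biopsies, the paired t-test on totals was significant in 71%, 34%, 19% or 9% of simulated trials for an assumed per-visit log-scale SD of 0.1, 0.2, 0.3 or 0.5. With a per-area density it was significant in 4 to 5% in all four cases.

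These rates show what would follow if such a shift occurred. The documents give no reason to expect one.

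**The case against.** The strongest reply is that the procedure is standardised. Forceps, site, size range and spacing are the same at all three sigmoidoscopies, so nothing in the documents suggests that tissue quantity differs systematically by visit. Random variation is modest once four biopsies and 10 participants are averaged. If other sources give the visit difference an SD of 30 to 50% (an assumption), adding 13.5% raises it only to √(0.30² + 0.135²) = 33% or √(0.50² + 0.135²) = 52%. This stands, and it limits the size of the point.

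Four stronger readings are tempting, and the documents do not support them.

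- *Smaller or shallower later biopsies would be read as neuron loss.* No section gives a biopsy depth or says that it changes, and a size difference could equally run the other way and hide a loss.
- *The varying number of biopsies drives the count.* The maximum of 20 is the number collected; four are assigned to staining. A shortfall matters only if fewer than four are stained or usable.
- *One biopsy without submucosa produces a 25% loss.* It takes 1/4 from one participant's total at one visit. With similar counts across 10 participants, that moves the group mean by 25%/10 = 2.5%.
- *There is plainly no control group.* Section 12.9 opens with a single set of samples from treated participants, yet also forms two matched groups of five, and Visit 3 speaks of randomization. The text contradicts itself. What can be said is that no untreated comparison is described, Section 15.2 declines a placebo, and the analysis is pre/post only.

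What remains is that the same forceps reduce variation in tissue quantity but do not remove it, and that the primary outcome has no unit.

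**Conclusion.** The point holds in limited form. As written, the primary outcome mixes tissue quantity with cell density, across a permitted 1.96-fold range in face area and with no control over the submucosa in the stained biopsies. The demonstrable cost is noise: about 9.5% on a four-biopsy total, 13.5% on one participant's visit difference and 4.3% on the mean of 10, given proportional counts and uniform diameters. Bias would need a systematic difference between visits. It could run in either direction, and the plan describes nothing that would detect it. The missing denominator is certain from the text; any actual bias is not. Power after a change of outcome cannot be calculated, because no SD is given for counts or densities. The change is worth making because it is cheap and removes most of the dependence on biopsy size.

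**What to change.** Define the primary outcome as neurons per mm² and, separately, glia per mm² of imaged submucosa. For each participant-visit, divide total cells by total submucosal area over the stained biopsies, and compare visits with the planned paired test.

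State these rules in advance:
- A biopsy without submucosa contributes neither cells nor area.
- A participant-visit with no submucosa in any stained biopsy is missing.
- If the log scale is used, say how zero counts are handled.
- Raw totals are reported as supportive.
- The four stained biopsies are per sigmoidoscopy, if that is what Lab Procedures means. Its wording is per participant, while each procedure visit allows up to 20 biopsies.

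Section 12.9 records that enrolment closed on May 24, 2024, and the study is open label (Section 10.1). Make the change before counts are compared between visits and report it as a late change, so that it cannot be taken for a choice of outcome made after seeing results.

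The cost is time to trace submucosal area on existing images or stained tissue, provided these are retained and cover the submucosa counted. No new participants or tissue are needed. Area density is not a complete correction: it does not fully allow for differences in the thickness of submucosa captured or for stretch when the tissue is pinned. Both should be stated as limitations.
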